Aim 3: Demonstrate target engagement by measuring BOLD responses evoked by TMS pulses to the right dIPFC during threat of shock.

Number of Subjects 75

**Main Inclusion
and Exclusion
Criteria**

Healthy volunteers, between 18 – 50 years old, free of psychological and neurological conditions, free of contraindications for TMS and MRI

Aim 1: Outcome measures. Fear potentiated startle (FPS) and Anxiety potentiated startle (APS) Statistical Analysis. The main analysis will be a 3 [stimulation: pre-stimulation vs. post-active vs. post-sham] by 2 [protocol: cTBS vs. iTBS] repeated-measures ANOVA.

**Statistical
Methodology**

Aim 2: Outcome measures. Accuracy and reaction time during the Sternberg Working memory paradigm. Statistical Analysis. The main analysis will be a 3 [stimulation: pre-stimulation vs. post-active vs. post-sham] by 2 [protocol: cTBS vs. iTBS] repeated-measures ANOVA.

Aim 3: Outcome measures. TMS-evoked BOLD activity during periods of acute fear and sustained anxiety. Statistical Analysis. BOLD maps will then be analyzed using a paired-sample t-test to compare BOLD responses evoked by active TMS and those evoked sham scalp stimulation.

**Data and Safety
Monitoring Plan**

The Principal Investigator is responsible for detecting, documenting, and reporting unanticipated problems (UPs), adverse events (AEs), including serious adverse events (SAEs), and deviations in accordance with IRB requirements and federal regulations.

CONFIDENTIAL

BACKGROUND AND STUDY RATIONALE

This study will be conducted in full accordance all applicable University of Pennsylvania Research Policies and Procedures and all applicable Federal and state laws and regulations including [as applicable include the following regulations as they apply 45 CFR 46, 21 CFR Parts 50, 54, 56, 312, 314 and 812 and Good Clinical Practice. All episodes of noncompliance will be documented.

Introduction

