This research is significant because upon completion, we expect to have direct evidence for a causal role of the right dIPFC in anxiety regulation, complete with evidence

CONFIDENTIAL

of target engagement through simultaneous TMS/fMRI, and a novel application to anxiety. This research will lay the groundwork for my long-term career objective, which is to develop an independent, NIH-funded research program employing psychophysiology, neuroimaging, and neuromodulation in healthy and anxious participants aimed at developing a circuit-level understanding of the neurobiological mechanisms underlying anxiety.

2 Study Objectives

Aim 1: Determine the effect of a 1-week course of TBS treatment (Continuous vs. Intermittent; right dlPFC target) on anxiety using the unpredictable shock-threat paradigm. Our hypothesis, consistent with our pilot data, is that strengthening circuits in the right dlPFC will facilitate anxiety regulation. Accordingly, we expect excitatory but not inhibitory TBS (compared to sham) to reduce induced anxiety.

Aim 2: Determine the effect of a 1-week course of TBS treatment (Continuous vs. Intermittent; right dlPFC target) on anxiety-related WM-deficits using the Sternberg WM paradigm during threat of shock. Our hypothesis is that the rTMS will strengthen right dlPFC circuits, which will rescue the anxiety-related WM deficits. Accordingly, we expect that 10 Hz rTMS (compared to sham) will improve accuracy on the Sternberg WM task during threat.

Aim 3: Demonstrate target engagement by measuring BOLD responses evoked by TMS pulses to the right dlPFC during threat of shock. Our hypothesis is that direct stimulation of the right dlPFC will reduce ongoing anxiety-related activity. Accordingly, we expect active but not sham TMS pulses to the right dlPFC to evoke BOLD deactivations in regions of the fear/anxiety network (i.e. amygdala, BNST, anterior insula).

3 Investigational Plan

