NPU Task: The instructed fear paradigm that will be implemented uses administration of predictable and unpredictable shocks to generate phasic and sustained forms of potentiated startle. We will use the NPU threat procedure as described in (Schmitz & Grillon, 2012). The experiment consists of three different conditions: no shock (N), predictable shock (P), and unpredictable shock (U), each lasting approximately 150 sec. In the N condition, no shocks will be delivered. In the P condition, shocks will be administered predictably, that is, only in the presence of a threat cue. In the U condition, the shocks will be unpredictable. In each 150-sec condition, an 8-sec cue will be presented four times. The cues will be different geometric colored shapes in each

CONFIDENTIAL

condition (e.g., a blue square for N, a red circle for P, and a green star for U) presented on a computer monitor in front of the subjects. The cue will signal the possibility of receiving a shock only in the P condition. It has no signal value in the N and U conditions. Instructions will also be displayed on a computer monitor to inform subjects of the nature of current condition by showing the following information throughout the testing procedure: “no shock” (N), “shock only during shape” (P), or “shock at any time” (U). During each predictable and unpredictable condition, one shock will be administered during the cue in the predictable condition and in the absence of a cue in the unpredictable condition.

There will be 2, 12 min runs during each test visit. Within each run, there will be 8 blocks (2 predictable, 2 unpredictable, 4 neutral). There are twice the number of neutral blocks to ensure that safe blocks alternate with threat (predictable or unpredictable) blocks. Startle probes will be presented either during the cue period, or the ITI. During the predictable and unpredictable blocks, there will be 2 trials per condition. Given that there will be twice as many neutral blocks, during these blocks there will only be 1 trial per condition. There will be a total of 3 shocks per run presented during either the ITI (unpredictable) or cue (predictable) periods.

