6.1 Primary Endpoints

Aim 1: Determine the effect of a 1-week course of TBS treatment (Continuous vs. Intermittent; right dlPFC target) on anxiety using the Neutral, Predictable, and Unpredictable (NPU) shock-threat paradigm.

Outcome measures. Fear potentiated startle (FPS) will be calculated by subtracting the blink magnitude during the predictable inter-trial interval (ITI) from the predictable cue. Anxiety potentiated startle (APS) will be calculated by subtracting the blink magnitude during the neutral ITI from the unpredictable ITI. Online anxiety ratings will be processed similarly.

Statistical Analysis. The main analysis will be a 3 [stimulation: pre-stimulation vs. post-active vs. post-sham] by 2 [protocol: cTBS vs. iTBS] repeated-measures ANOVA. In addition to the main factors considered, we may also co-vary out several individual difference measures (e.g. baseline anxiety via self-report questionnaires, counterbalance order, overall stimulation accuracy, and Sternberg working memory (WM) performance to assess target engagement).

Aim 2: Determine the effect of a 1-week course of TBS treatment (Continuous vs. Intermittent; right dlPFC target) on anxiety-related WM-deficits using the Sternberg WM paradigm during threat of shock.

Outcome measures. During each Sternberg trial, subjects will see a series of 5 or 8 letters presented singularly (encoding period) that will be followed by a brief interval where subjects are required to maintain these letters (maintenance period). At the end of the maintenance period, subjects will indicate whether the position of the letter in the series matches the number. Accuracy will be scored as the percent correct for each trial type.

Statistical Analysis. The main analysis will be a 3 [stimulation: pre-stimulation vs. post-active vs. post-sham] by 2 [protocol: cTBS vs. iTBS] repeated-measures ANOVA. As with Aim 1, we may also include several other individual difference measures as covariates in this analysis.

Aim 3: Demonstrate target engagement by measuring BOLD responses evoked by TMS pulses to the right dlPFC during threat of shock.

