Outcome measures. Standard Multi-echo fMRI preprocessing will be conducted using the AFNI software package. Steps include: slice-time correction, despiking, volume registration, TE-dependent ICA denoising (to remove non-BOLD artifacts), masking, blurring, scaling, motion scrubbing, T1-EPI alignment, normalization (using MNI template). At the first level, variable duration mini-blocks will be used to model BOLD activity during the maintenance interval of the Sternberg trials. Motion parameters and all other events will be included in the model as regressors of no interest.

Statistical Analysis. Whole-brain maps will be created for contrasts mirroring those used to create FPS and APS in Aim 1. FP-BOLD and AP-BOLD maps will then be analyzed using a paired-sample t-test to compare BOLD responses evoked by active TMS and those evoked sham scalp stimulation. Monte Carlo simulations will be conducted to cluster-correct the results using a voxelwise p-value threshold of 0.001, a cluster alpha of 0.05, and a realistic spatial autocorrelation function to model the noise. This is the standard approach implemented in AFNI following the influential Eklund et al. 2016 paper. As with Aim 1, we may also include several other individual difference measures as covariates in this analysis.

CONFIDENTIAL

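### The Aim 3 contrasts test whether the pulse effect differs between threat and comparison periods; alone, they cannot show the deactivation that the objectives predict

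*Combined protocol and SAP*

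**What the plan says.** The aim, as restated in section 6.1, is: "Demonstrate target engagement by measuring BOLD responses evoked by TMS pulses to the right dlPFC during threat of shock". Sections 2 (Study Objectives) and 3.2 (Study Endpoints) give the hypothesis that direct stimulation "will reduce ongoing anxiety-related activity". From it they derive an operational prediction: active but not sham pulses are expected "to evoke BOLD deactivations in regions of the fear/anxiety network (i.e. amygdala, BNST, anterior insula". The Study Summary names the outcome as "TMS-evoked BOLD activity during periods of acute fear and sustained anxiety", without a sign and without a subtraction. Section 3.1 makes the BOLD response to the pulses the primary outcome measure of this aim.

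Section 6.1 then defines the maps to be analysed: "Whole-brain maps will be created for contrasts mirroring those used to create FPS and APS in Aim 1". The startle definitions being mirrored are:

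- FPS: "Fear potentiated startle (FPS) will be calculated by subtracting the blink magnitude during the predictable inter-trial interval (ITI) from the predictable cue".
- APS: "Anxiety potentiated startle (APS) will be calculated by subtracting the blink magnitude during the neutral ITI from the unpredictable ITI".

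The resulting FP-BOLD and AP-BOLD maps are compared between active and sham with a paired t-test.

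Section 5.1.9 replaces the startle probes, which fall in cue and ITI periods, with single TMS pulses. There is one active run and one sham run, and sham is made with a 4 cm spacer. On the predictable condition it says: "The cue will signal the possibility of receiving a shock only in the P condition". The predictable ITI is therefore free of shock risk, as is the neutral ITI.

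No section plans a test of the active response under threat against a baseline, a comparison of active with sham within threat, or a check on the sign of the component responses.

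**The concern.** The prediction concerns the sign of a response: an active pulse pushes the signal down during threat and a sham pulse does not. The planned analysis concerns a difference of differences. Because pulses are delivered in both the threat period and the comparison period, each subtraction contains a pulse-evoked response in both of its terms. Whatever the pulse does equally in the two periods drops out, and the sign of what remains does not give the sign of the response under threat.

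Aim 3 stands under Primary Endpoints and is the trial's evidence of target engagement; sections 1.1 and 10.3 expect it to support a causal role of the right dlPFC. With the planned contrast alone, a null result would not rule out deactivation and a negative result would not demonstrate it.

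**Working it through.** The plan gives no figure to reproduce here. Section 6.2 makes one power calculation for the whole study and none specific to Aim 3. The check is algebra on the plan's own definitions.

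**Step 1: the tested quantity.** Let A_t and A_c be the active-pulse responses in the threat and comparison periods, and S_t and S_c the sham responses. For FP-BOLD, t is the predictable cue and c the predictable ITI. For AP-BOLD, t is the unpredictable ITI and c the neutral ITI. The paired t-test addresses

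D = (A_t - A_c) - (S_t - S_c).

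**Step 2: what D can and cannot distinguish.** The response values below are illustrative, in arbitrary units; the documents give none.

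| Case | A_t | A_c | S_t | S_c | D (planned) | A_t - S_t | Deactivated under threat? |
|---|---|---|---|---|---|---|---|
| a | -0.3 | -0.3 | 0 | 0 | 0.0 | -0.3 | yes |
| b | -0.3 | 0 | 0 | 0 | -0.3 | -0.3 | yes |
| c | +0.2 | +0.4 | 0 | 0 | -0.2 | +0.2 | no |
| d | 0 | +0.3 | 0 | 0 | -0.3 | 0.0 | no |
| e | +0.2 | +0.1 | +0.5 | +0.1 | -0.3 | -0.3 | no |
| f | -0.2 | -0.4 | 0 | 0 | +0.2 | -0.2 | yes |

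- Case a: the deactivation cancels exactly, whatever the sample size.
- Cases b, d and e give the same D, but only b contains a deactivation.
- Case c gives a negative D from two activations.
- Case f gives a positive D although the response under threat is negative.
- Active minus sham within threat deals with cases a, c, d and f but is still misled by case e. Only A_t against a baseline separates e from b. Both added tests are needed.

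**Step 3: sensitivity.** Let the active response be -d in threat and -r·d in the comparison period, with sham 0. Then D = -d + r·d = -(1-r)d. Let each estimate have standard deviation s, with correlation rho between the two periods of one run and independence between runs.

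- SD of D = 2s·sqrt(1-rho).
- SD of A_t - S_t = s·sqrt(2).
- Standardised effect of D relative to the within-threat comparison = (1-r)/sqrt(2(1-rho)).

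Neither r nor rho is in the documents. Over an assumed range:

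| r | rho = 0 | rho = 0.5 | rho = 0.7 |
|---|---|---|---|
| 0 | 0.71 | 1.00 | 1.29 |
| 0.5 | 0.35 | 0.50 | 0.65 |
| 0.8 | 0.14 | 0.20 | 0.26 |
| 1 | 0 | 0 | 0 |

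Only the last row is independent of rho. For a purely threat-specific effect (r = 0), the planned contrast is the more sensitive one once rho exceeds 0.5.

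**Step 4: illustration.** A single-voxel simulation assumed n = 56 (the completer target, an upper limit because the TMS/fMRI visit is optional), s = 0.3, rho = 0, two-sided p < 0.001 and no cluster step. D was significantly negative in 0.04% of runs in case a, 60% in case b and 18% in case c. A_t - S_t was significantly negative in 96% of runs in cases a and b, and also in 96% in case e, where there is no deactivation. These percentages depend on the assumed values. With rho = 0.5, for example, the SD of D is 2 × 0.3 × sqrt(0.5) = 0.42. That equals the SD of the within-threat comparison, 0.3 × sqrt(2) = 0.42, so the 60% in case b would also be about 96%.

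**The case against.** The strongest reply is that the interaction is the right test. The hypothesis is about activity related to anxiety, which can fairly be read as activity under threat relative to safety. On that reading, a pulse that damps the insula equally in neutral periods has not regulated anxiety, and a null AP-BOLD result is correct. The mirroring is also deliberate: section 5.1.9 says that pulses replace probes so that evoked BOLD can be set beside the startle pattern. The subtraction has a technical merit too. Active and sham are separate runs, and the spacer may not match coil or scalp sensation. Within-run differencing removes run-order effects, drift and such mismatches where they are common to both periods; a within-threat comparison of active with sham keeps them.

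All of this stands, and it is the reason to keep FP-BOLD and AP-BOLD. It does not close the gap, because the operational prediction that follows the hypothesis is still an evoked deactivation in active but not sham, and D cannot verify it.

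Four stronger readings are tempting and are not supported:

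- A reader might infer that section 6.1 tests something unrelated to the hypothesis and that the endpoint should be replaced. The hypothesis sentence and the stated link to startle argue against that.
- A reader might infer a definite loss of power. That holds only for given r and rho, and neither is stated.
- A reader might infer that the investigators will report a smaller activation as success. The documents give no directional success rule for Aim 3. They do not prevent that reading, but they do not announce it.
- A reader might take the negative sign to be part of the synopsis. It appears only in sections 2 and 3.2.

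**Conclusion.** The point holds in a limited form. The Aim 3 analysis in section 6.1 is a valid test of threat specificity, but on its own it cannot establish the deactivation that sections 2 and 3.2 predict. Two consequences are certain because they follow from the definitions: a deactivation of equal size in both periods yields exactly 0, and a negative contrast is compatible with no deactivation at all (for example -0.2 from active responses of +0.2 and +0.4 with sham at 0). The size of any sensitivity loss is not certain. It is (1-r)/sqrt(2(1-rho)) under equal variances and independent runs, and it can exceed 1.

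This limits what Aim 3 can conclude. It does not affect Aims 1 and 2 or the conduct of the trial. Aim 3 is mechanistic and rests on an optional visit in a pilot study, but it is listed as a primary endpoint, and the correction needs no new data.

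**What to change.** In section 6.1, keep FP-BOLD and AP-BOLD, active versus sham, as the test of threat specificity, and add from the same runs:

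1. The pulse-evoked response in the unpredictable ITI (anxiety) and in the predictable cue (fear), each tested for active against sham and for active against the model baseline. That is 2 periods × 2 tests = 4 added contrasts.
2. A first-level model in which the TMS pulses are events of interest, with the baseline defined. Section 6.1 currently describes a model of the Sternberg maintenance interval and treats all other events as of no interest, so the regressors that any of these contrasts need are not specified.
3. A claim rule. Deactivation is claimed only if the active response under threat is below baseline and below sham. Threat-specific engagement is claimed only if FP-BOLD or AP-BOLD also differs between active and sham.

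The cost is analysis-plan wording and computation on runs already planned. Requiring both tests within a period needs no further alpha adjustment, but making claims across two periods and alongside the interaction does, and the plan should say how. The deactivation claim becomes slightly harder to meet. The within-threat comparison of active with sham keeps run-order and spacer differences, so it should be reported together with the interaction and not in its place.

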3.1 General Design

Aims 1 and 2 of this project will be tested using a between-subjects design where 1 group of healthy volunteers will receive 4-day courses of active and sham cTBS stimulation to the right dlPFC, while the other group will receive 4-day courses of active and sham iTBS stimulation to the right dlPFC. In Aim 1, we will test the effects of this stimulation on anxiety during the NPU threat task. In Aim 2, we will test the effects of this stimulation on anxiety-related WM deficits using the Sternberg WM paradigm. In addition, we will also administer several self-report questionnaires to assess their baseline (pre-stimulation) anxiety. Subjects will be randomly assigned to groups, and the order of stimulation (active vs. sham) will be counterbalanced across subjects. Aim 3 will be tested using a within-subjects design where this same group of subjects will receive single-pulse active and sham stimulation to the right dlPFC during the NPU threat task while in the MRI scanner. BOLD activity to the TMS pulses will be the primary outcome measure.

Subjects will undergo 12 study visits spaced over a 4-week period (Figure 3). Subjects may also be offered an optional 13th visit where TMS/fMRI is conducted. On Week 1,

CONFIDENTIAL

subjects will undergo a pre-stimulation behavioral visit where they complete the NPU threat task and the Sternberg WM paradigm, and a pre-stimulation MRI visit where they undergo all the structural and functional imaging needed to identify the optimal target of stimulation for the course of TMS used in Aims 1 and 2. This information will be used to perform neuronavigation during the study visits to ensure accurate target stimulation. Subjects will complete the TMS/fMRI scans needed for Aim 3 during the optional visit. On Weeks 2 and 4, subjects will undergo 5 visits. The first 4 visits will be stimulation visits where they receive either active or sham stimulation while doing the Sternberg WM task. On the 5th visit, they will return for the post-stimulation test visit, where they will complete the NPU threat task and the Sternberg WM paradigm.

[figure not shown]

Figure 3: Timeline showing subject visits in the proposed project.

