6.2 Sample Size and Power Determination

Because we have several outcome measures, and because there is little known about how TMS will affect these outcome measures, we are conducting a single power analysis to determine sample size, based on a moderate effect size of ($f=0.5$). If we set power at 0.8 and use a corrected two-tailed alpha of 0.025 we would need 26 subjects per group to detect a main effect. Assuming a 15% unusable data rate and 3 pilot subjects, we will need 63 total subjects. However, this will be updated prior to enrollment based on the best available information at the time. To ensure that we are adequately powered across the study arms, and to account for additional dropout due to scheduling issues, we plan to recruit up to 75 participants.

7 Safety and Adverse Events

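### Aim 3 tests two unranked whole-brain maps, each at cluster alpha 0.05, with no error control across them: up to about a 9.75% chance of a false cluster in at least one map

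*Combined protocol and SAP*

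**What the plan says.** Aim 3 is listed in Section 6.1, Primary Endpoints, and Section 3.1 states for it that "BOLD activity to the TMS pulses will be the primary outcome measure".

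The analysis in Section 6.1 has two maps: "Whole-brain maps will be created for contrasts mirroring those used to create FPS and APS in Aim 1". For startle, the fear contrast (FPS) is obtained by "subtracting the blink magnitude during the predictable inter-trial interval (ITI) from the predictable cue", and the anxiety contrast (APS) by "subtracting the blink magnitude during the neutral ITI from the unpredictable ITI". Then "FP-BOLD and AP-BOLD maps will then be analyzed using a paired-sample t-test", active against sham, with cluster correction by Monte Carlo simulation "using a voxelwise p-value threshold of 0.001, a cluster alpha of 0.05, and a realistic spatial autocorrelation function to model the noise".

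The section does not rank the maps, divide alpha between them, state sidedness, or say whether one positive map or both are needed.

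The expected finding is narrower than the test. Section 2 (repeated in 3.2) expects active but not sham pulses "to evoke BOLD deactivations in regions of the fear/anxiety network", naming the amygdala, BNST and anterior insula. The analysis text carries neither that direction nor those regions.

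Section 6.2 gives the existence of several outcome measures as a reason for running one power analysis, and sets out to "use a corrected two-tailed alpha of 0.025". It does not list the outcomes that the correction covers.

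**The concern.** A cluster alpha of 0.05 limits the chance of any false cluster among the voxels of one map. It says nothing about a second map. The Study Summary and Section 5.1.9 treat fear and anxiety as parallel targets, while Aim 3 makes one claim: that the target was engaged. Two unranked chances at one claim are a multiplicity problem unless the plan says how the results combine.

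The claim carries weight. Sections 1.1 and 10.3 present evidence of target engagement as a principal product of the study. With the decision rule left open, a cluster in either map, of either sign, in any region, could later be put forward as that evidence. The plan gives a reader no stated error rate against which to judge it.

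**Working it through.** **Inputs.** From Section 6.1: two maps; voxelwise p 0.001; cluster alpha 0.05, naturally read as applying to each map; no ranking; sidedness not stated. From Section 6.2: a two-tailed alpha of 0.025.

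**The plan's own figures.** The plan gives no error rate across the two maps, so there is none to reproduce. The 0.025 equals 0.05/2, a two-test Bonferroni level. It appears only in the sample-size calculation for a main effect (f = 0.5, power 0.8, 26 per group). Those inputs give 21 per group for two groups by the noncentral F (20 by the normal approximation), and 26 per group gives about 90% power. That mismatch is a separate matter and does not enter the error rates below.

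**Chance of at least one false cluster in either map, when neither has an effect.**

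- Independent maps: 1 - (1 - 0.05)² = 1 - 0.9025 = 9.75%.
- Upper bound under any dependence: 0.05 + 0.05 = 10%.
- Positively correlated map-level statistics (bivariate normal): 9.3% at correlation 0.3, 8.8% at 0.5, 8.0% at 0.7, 6.8% at 0.9, 5.0% at 1.

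The documents do not give the correlation, so it is an assumption. The two contrasts share no condition: one is predictable cue minus predictable ITI, the other unpredictable ITI minus neutral ITI. A simulation of 2,500 pairs of smooth three-dimensional null fields, cluster-thresholded at a pooled per-map error of about 4.7%, gave an either-map rate of 9.4% to 9.7% for voxel correlations from 0 to 0.7. Correlation between voxels therefore lowers the figure little.

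**Chance of a false target-engagement claim.** This depends on rules that the plan does not state. Independence is assumed where a product is used, and in the second row the cluster error is assumed to split evenly between signs.

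| Reading of Section 6.1 | Calculation | Rate |
|---|---|---|
| Any cluster, anywhere, either map; 0.05 covers the whole test of each map | 1 - 0.95² | 9.75% |
| Two-sided 0.05, only deactivations count, either map | 1 - 0.975² | 4.94%, lower within the three named regions |
| Both maps required | no more than one map's error | at most 5% (0.05² = 0.25% if neither map has an effect) |
| Each sign run separately at 0.05, either sign and either map | 1 - 0.95⁴ | 18.5% |

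**After splitting alpha.** With 0.025 per map: 1 - 0.975² = 4.94% if independent, and 0.025 + 0.025 = 5% at most. The exact independent-case level is 1 - √0.95 = 0.0253, so 0.025 gives up almost nothing. This holds only if 0.025 covers both signs of a map. Running each sign separately at 0.025 would give 1 - 0.975⁴ = 9.6%, which is why sidedness has to be stated as well.

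**The case against.** The strongest reply is that 9.75% is not the error rate of the claim that matters. Sections 2 and 3.2 predict deactivation in three named regions, so a false activation, or a cluster elsewhere, would not match the prediction. **This stands.** A reader might infer that the chance of a false target-engagement claim is 9 to 10%. The documents do not support that, because no section says that one cluster of any kind suffices. Equally, no section imposes the restrictions that would bring the rate down, and one permissible reading nearly doubles it.

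A second reply concerns Section 6.2. A reader might infer that the 0.05 in 6.1 contradicts the 0.025 in 6.2, so that a cluster at corrected p = 0.04 passes one section and fails the other. The documents do not support that either. The 0.025 is a planning alpha for a main effect with a size per group, whereas Aim 3 is a within-subject paired comparison. The correction could equally refer to FPS and APS, to accuracy and reaction time, or to Aims 1 and 2. What remains is that the study recognises several outcomes as a reason to correct, and that no analysis in 6.1 applies the corrected level.

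Third, fear and anxiety are different questions, the study is labelled a pilot, and the Aim 3 scans come from an optional visit. Two separately reported claims at 0.05 each would be defensible. The plan, however, states one claim for Aim 3, and does not say that the maps will be interpreted separately.

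Finally, the first-level model in 6.1 is described for Sternberg maintenance intervals, with all other events as nuisance regressors. As written it does not yield the TMS-evoked NPU contrasts. That needs its own correction, but it does not remove the question of how the two maps share error.

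**Conclusion.** The point holds as a gap in multiplicity control. Two unranked maps serve one claim, each is naturally read as tested at cluster alpha 0.05, and nothing controls error across them. The chance of at least one false cluster in either map is up to about 9.75%, with a hard limit of 10%, against 5% within a single map. This assumes that the cluster procedure attains its nominal level, that the 0.05 covers the whole test of each map, and that neither map has a true effect.

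The chance of a false target-engagement claim cannot be determined from the plan. It is about 5% or less if both maps are required, or if the test is two-sided and only deactivations count. It is about 18.5% if each sign is tested separately at 0.05. The relation to Section 6.2 is a gap between planning and analysis alpha.

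This is a cheap improvement to make before the Aim 3 data are analysed, and it does not undermine the design.

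**What to change.** In Section 6.1, Aim 3, do one of the following:

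- Set the cluster alpha to 0.025 for each of FP-BOLD and AP-BOLD, keeping voxelwise p 0.001. Either-map error is then at most 5%.
- Name AP-BOLD as the deciding map at cluster alpha 0.05 and make FP-BOLD secondary. The Section 2 hypothesis for Aim 3 concerns ongoing anxiety-related activity, which is what AP-BOLD measures.

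In either case, state whether the test is one- or two-sided, with the cluster alpha covering the whole test of a map. State also that a claim of target engagement requires deactivation, active relative to sham, in the amygdala, BNST or anterior insula, and specify how many of these regions are needed. One sentence in Section 6.2 should say which outcomes its corrected alpha covers.

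No new data, visits or subjects are needed. The first option reads the Monte Carlo cluster-size threshold at 0.025, so the minimum cluster is slightly larger and power per map slightly lower. The second costs AP-BOLD no power, but FP-BOLD can then only support the claim as a secondary result.
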